### **EVestG Measurement**

All study participants (in all three groups) will go through four sessions of EVestG assessments: 1) before rTMS treatment, 2) after 12 sessions of rTMS treatment, 3) four weeks after the last rTMS treatment, and 4) eight weeks after the last rTMS treatment.

The subjects sit in a hydraulic chair with their eyes closed and head rested on the chair headrest; they receive a series of orthogonal passive whole body movement stimuli: up/down translation and a horizontal rotation to the right and return to center (RTC) in both sitting upright and supine positions, and side tilts to the right and left.

Each tilt and the rotation are about 40 degrees, while up/down movement are about eight inches; the movements are designed to be smooth with a constant acceleration/deceleration over 3s. The recordings are made in an acoustically attenuated (>30dB) and electromagnetically shielded chamber at the EVestG Lab, Riverview Health Center. The active gelled recording electrodes are TM-EcochGtrode (Bio-logic, France), and placed in both ears proximal to the eardrum. Reference electrodes (Biopac EL254S for earlobe and EL258S for forehead) are placed on the ipsilateral earlobes and a common ground electrode is placed on the forehead.

The left and right ears' signals are recorded using Spike2 software via a CED-1902 amplifier (60Hz notch filter, 10k gain, 1Hz high pass filter) and digitized using CED1401 ADC board at sampling rate of 41,666Hz. Each recording's duration was 60s for each stimulus: 20s stationary at the center position, 3s motion to a position (up or rotated), 17s stationary in that position, 3s return to the center, and another 17s of stationary recording in the center position.

The chair's position is also recorded simultaneously with the ear signals; it is used to extract the segments of interest for analysis. The particular segments of interest, shown in Figure 2, are: 1.5s immediately prior to the movement (BGi), 1.5s acceleration (onAA) and 1.5s deceleration (onBB) as well as the 1.5s segments from the return to the center: RTC BGi, RTC onAA and RTC

onBB. The acceleration/deceleration segments are selected as they give the largest differences compared to background. Each EVestG recording may take up to one hour.

### **Standard Neuropsychological and Screening Measures**

The neuropsychological assessments include: Rivermead Post Concussion Symptoms Questionnaire (RPQ) [7,59], Montreal Cognitive Assessment (MoCA) [60], Montgomery Asberg Depression Rating Scale (MADRS) [61] and Stroop tasks [62]. Patients with TBI will go through all above mentioned assessments four times, similar to EVestG assessments. The healthy Control Group will go through only MoCA and MADRS assessments at the beginning of the study and at the last assessment session.

### **Custom Designed Visuo-Spatial and Spatio-Temporal Assessments**

Our custom designed visuo-spatial and spatiotemporal assessments include our virtual reality navigational orientation assessment [63].

[figure not shown]
### **Data analysis**

**EVestG Biofeature Extraction** – The NEER algorithm [52] will be used to locate and extract vestibular neural events. The interval histograms of the neural events are also used to extract the basic statistical properties of the neural firings such as probability density function (pdf), mean and variance, as well as fractal dimension, kurtosis and skewness of the signal. The features extracted from all tilts will be investigated to determine biofeatures specific to a concussion. The extracted biofeatures, e.g. fractal dimension, kurtosis and skewness of the potentials' distribution, from the recorded signal will be compared between Sham and Treatment Groups.

[figure not shown]
**Statistical Analysis, Clustering, Decision Making and Validation** – After data collection, the multivariate Analysis of Variance (MANOVA) statistical test will be run to determine the significant differences of any of the extracted biofeature measures between the sessions and the Control Group and the Treatment and Sham Groups. In all instances, a p-value less than 0.05 is considered significant. Cross correlation analysis will also be used to find the correlation between these measures and the neuropsychological assessments scores. Once the statistically significant features among the groups are found, the classic approach of discriminant analysis with leave-one-out routine (for robust results in small size data) will be run to investigate whether concussion cases can be identified. An important issue to address is the membership assignment of the subjects. Since there may not be confirmed and solid clinical and neuropsychological assessments for the recovery from the TBI post-symptoms, we will also run unsupervised (blind) clustering of the objective measures followed by our recently developed diagnostic decision making algorithm to identify TBI recovery. The diagnostic and monitoring algorithms will be checked with the updated diagnoses of the clinical symptoms (by the referring physician) and the neuropsychological evaluations.

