### Theme 1: Applying rTMS treatment and its evaluation by neuropsychological and clinical assessments

1. Recruit people (from Riverview Health Center and also from [name] referrals), who have had a head injury within the past two to 12 months, have a clear diagnosis of TBI, and have persistent post-TBI symptoms. Collect standard neuropsychological assessment data at baseline.

2. Enroll the study participants into a “Sham Group” and a “Treatment Group” with a three-week protocol, and apply the treatment.
3. Record spatio-temporal assessments before and after treatment sessions, and examine the efficacy of rTMS treatment on the post-TBI symptoms by standard clinical and neuropsychological assessments by statistical analysis.

Theme 2: Monitoring treatment efficacy by objective measures, EVestG and spatio-temporal assessments

4. Record EVestG data with all its seven current stimuli at baseline (before the treatment) and immediately after treatment and also four and eight weeks after the last treatment.
5. Analyze EVestG data for extracting the optimum measures (biofeatures) showing the changes due to rTMS treatment.
6. Optimize (reduce the number of stimuli if possible) the EVestG recording protocol upon the results of Objective 5.
7. Examine the statistical correlation of the EVestG biofeatures representing the TBI recovery with data from the clinical and neuropsychological assessments as well as spatio-temporal assessments (derived in Objective 3).

Theme 3: Evaluating the objective measures of EVestG and spatio-temporal assessments in Control group

8. Recruit 20 age-and-gender-matched individuals with no history of head injury and record their EVestG data four times with a similar schedule to that of TBI patients, and investigate the consistency of the EVestG data between the sessions and compare with those of people with TBI during treatment.
9. Run the spatio-temporal assessments at the same sessions of EVestG recording in the Control Group and examine the effect of learning on the performance in these assessments.

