### **Study Protocol**

#### **Study Population/Participants**

A total of 20 individuals with a clear diagnosis of TBI within the last 12 months (as confirmed by their treating Neurologist, Psychiatrist or Medical Rehab Physiatrist, who are the co-investigators in this study) prior to the commencement of this study will be recruited from Riverview Health Center patient and [name] clinic patient population. Ten patients will be randomly assigned to **Treatment Group** and 10 others to **Sham Group**. Neither the patients, nor the clinical assessors will know the sham versus real treatment group assignment. In addition, as one of the objectives of this study is to evaluate the EVestG assessment as a

diagnostic and monitoring tool, 20 age-and-gender-matched cognitively healthy volunteers will be recruited as controls for the EVestG assessment. The healthy **Control Group**'s participants must not have any history of TBI and also meet other exclusion criteria for patients group listed below.

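### Nothing in the planned Treatment v Sham EVestG comparison separates movement towards healthy-control values from movement away, so a significant difference cannot by itself be read as recovery

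*Combined protocol and SAP*

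**What the plan says.** The Proposal Summary and the heading of Theme 2 make EVestG an objective measure of treatment efficacy and recovery, used alongside clinical assessments. Under Data analysis, EVestG Biofeature Extraction, the features "from the recorded signal will be compared between Sham and Treatment Groups". The next paragraph names the test: "the multivariate Analysis of Variance (MANOVA) statistical test will be run to determine the significant differences of any of the extracted biofeature measures", across sessions and across the Control, Treatment and Sham Groups. The threshold is general: "In all instances, a p-value less than 0.05 is considered significant".

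In the Objectives, Objective 5 is to analyse the recordings for "extracting the optimum measures (biofeatures) showing the changes due to rTMS treatment". Objective 7 then correlates "the EVestG biofeatures representing the TBI recovery" with clinical, neuropsychological and spatio-temporal results. The Background expects EVestG signals to change after TBI but does not say which way.

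The groups are 10 Treatment, 10 Sham, and a healthy reference: "20 age-and-gender-matched cognitively healthy volunteers will be recruited as controls for the EVestG assessment". Table 1 schedules EVestG for all three groups at weeks 0, 4, 8 and 12. No power, effect size, SD or number of features is stated.

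**The concern.** A change under rTMS is recovery only if it goes from the injured state towards the healthy one. A feature that does not differ between TBI patients and Controls at week 0 has nothing to recover, and a feature that does differ can be pushed further from healthy. The MANOVA cannot tell these cases apart, and the step from Objective 5 to Objective 7 passes from change to recovery without asking. This would be so even if the features had been fixed in advance from other data.

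At stake is what a significant EVestG difference means. It could be recovery, worsening, or a non-specific effect of stimulation. With small arms, several features and no stated direction, whichever sign appears can be described as recovery afterwards.

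**Working it through.** **1. Does any planned step set a direction?** Taking the candidates in turn:
- *Search for concussion-specific features (Data analysis).* No session, order or sign is given, and the Sham v Treatment sentence refers to the extracted features, not to a concussion-specific subset.
- *Controls in the MANOVA.* An omnibus rejection does not say whether Treatment moved towards or away from them.
- *Correlation with clinical scores (Objective 7 and Data analysis).* No expected sign is stated.
- *Discriminant analysis.* It is planned to identify concussion cases, not to score change under treatment.
- *Clustering and the check against updated diagnoses.* Clustering has no healthy direction unless one is stated, and the plan itself allows that solid clinical markers of recovery may be lacking.

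None sets a direction.

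**2. Is the test sign-blind in practice?** At 10 v 10 and alpha 0.05, simulated shifts of +1 SD and -1 SD in one feature are rejected 56.4% and 56.2% of the time (two-sided t test). With three independent features, each shifted by +0.6 or -0.6 SD, the two-group MANOVA (Hotelling T²) rejects 38.3% and 37.5%. The differences are simulation error.

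**3. What would a directed score do?** The plan gives no figure to reproduce, so these inputs are assumptions: no dropout, independent features, visit-to-visit correlation r = 0.7, and a week-0 TBI-Control gap D = 2.07 SD. That gap solves Φ(D/2) = 0.85. The 85% is borrowed from the Background, which does not attribute it to TBI. rTMS is assumed to close half the gap relative to sham.
- SD of change = √(2(1 − 0.7)) = 0.775.
- Standardised shift d = (2.07/2)/0.775 = 1.336.
- MANOVA noncentrality = (10/2) × 1.336² = 8.93. With p and 19 − p degrees of freedom, power is 68.5%, 44.6% and 22.7% for p = 2, 5 and 10.
- A two-sided t test along the true axis (18 df) would have 80.7% power.

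Estimating the axis from 20 TBI v 20 Control recordings at week 0 costs some of that. By simulation:

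| Case | Features | MANOVA | Week-0 score |
|---|---|---|---|
| Half-gap closure, gap 2.07 SD | 2 / 5 / 10 | 69 / 46 / 23% | 78 / 73 / 64% |
| Same, gap 1.5 SD | 2 / 5 / 10 | 41 / 26 / 13% | 52 / 45 / 34% |
| Same, gap 1.0 SD | 2 | 20% | 25% |
| Gap 2.07 SD, effect 45° off the axis | 2 / 5 / 10 | 66 / 44 / 22% | 49 / 44 / 38% |
| Gap 2.07 SD, effect 60° off the axis | 2 / 5 / 10 | 69 / 42 / 24% | 30 / 28 / 24% |

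If rTMS instead moves patients half a gap away from Control (gap 2.07 SD), the MANOVA is significant 70/45/23% of the time. The score shows a significant shift towards Control in 0% of trials. With no effect, the score rejects in about 4 to 6% of trials.

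**4. Limit of a linear score.** It keeps rising after patients pass the Control mean. A shift of twice the gap ends as far beyond Control as patients began below it, yet it scored as recovery in 100% of trials. The score therefore needs an overshoot check.

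**The case against.** This is a pilot, and Objective 5 is feature discovery, for which an undirected omnibus test is defensible. Control recordings, clinical correlations and the check against diagnoses are all planned, so a shift away from Control would be visible in the data. This stands as a reason to keep the MANOVA. It does not supply a rule, fixed beforehand, for reading the direction.

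A reader might infer that a shift away from healthy would count as efficacy. The documents do not support that. Objective 3 examines efficacy by clinical and neuropsychological assessments, EVestG runs in parallel with these, and the later offer of treatment to the Sham Group already requires improvement over placebo. No rule turns EVestG significance alone into an efficacy claim.

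A reader might also infer that power is lost because the test is two-sided. It is not: a one-sided test at 0.025 has essentially the same power as a two-sided test at 0.05 (56.2% for both at d = 1.0), and the score proposed here is itself tested two-sided. Its gain comes from testing one axis instead of many, and it requires that rTMS act near the TBI-to-Control axis, which no section of the plan asserts.

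**Conclusion.** The concern holds as a defect of interpretation. The Treatment v Sham comparison is sign-blind, and nothing planned separates movement towards Control from movement away, so a significant EVestG difference cannot by itself be read as recovery. That conclusion rests on the text and on none of the assumed inputs.

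The power benefit is conditional. With the effect on the axis and a 2.07 SD gap, it is about 9, 27 and 41 percentage points for 2, 5 and 10 features (78 − 69, 73 − 46, 64 − 23). At a 1.0 SD gap with 2 features it is 5 points. At 45° off the axis the score loses with 2 features, ties with 5 and wins only with 10; at 60° it never wins. Gap, correlation, feature count and independence are all assumptions. The plan should be changed for the sake of interpretation, with any power gain a secondary benefit.

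**What to change.** In Data analysis, add a recovery analysis of Treatment v Sham:
- Fix a short feature list beforehand. From week-0 recordings only, fit the TBI (20) v Control (20) discriminant direction. It is set before any stimulation, so it favours neither arm.
- Apply it unchanged at weeks 4, 8 and 12, and compare Treatment v Sham on change in the score with a two-sided test.
- State that a difference supports recovery only if Treatment moves from the week-0 TBI mean towards the Control mean. Report each arm's mean against the Control mean, and do not read a shift away from Control, or well past it, as recovery.
- In Objective 7, state the expected sign of each correlation: movement towards Control with lower RPQ and MADRS, and with better MoCA and Stroop.
- Keep the MANOVA beside the score for effects off this axis.

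The cost is wording and a few lines of code. No new data are needed, since the week-0 recordings are already scheduled and discriminant analysis is already planned. The downside is that the score can have less power than the MANOVA for off-axis effects, which is why both are kept.

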## Introduction

### a. Rationale

Traumatic brain Injury (TBI) occurs when a sudden trauma causes either transient or permanent brain damage. In some literature, the term “concussion” is used to refer to the most common (mild) type of TBI. It is defined as an immediate and transient impairment of neural functions, such as the alteration of consciousness, balance and/or visual disturbances, due to a direct blow to the head or after a blow elsewhere that is transmitted to the head. In other literature, mostly neurological journals (and in this proposal), mild TBI (mTBI) and concussion are used interchangeably.

Every three minutes, there is a TBI case in Canada [3], and 50,000 Canadians sustain brain injuries each year [4]. Motor vehicle crashes and traffic-related incidents are major causes of TBI; 40% of TBI cases in Manitoba are due to car accidents [5]. Transport Canada reports that the road accident rate of the province of Manitoba is greater than the national average [6]. According to MPI’s 2011/12 annual report, there was an 89% increase in brain injury claims from 146 in 2010/11 to 276 in 2011/12 [5].

The majority of patients with mTBI recover in the first 2-4 weeks; the recovery time is much longer (a few years) for those with severe TBI. In general, the fastest improvement occurs in the first six months after injury and the patient may continue to get better over a period of up to two years. However, many survivors of severe TBI and mTBI continue to experience disabling persistent post-TBI symptoms including somatic and emotional symptoms (sleep disturbances, fatigue, headache and emotional changeability) [7], as well as cognitive [8,9], visual [10-15], and vestibular abnormalities [16,17]. Any of these adverse consequences of TBI impact the individual's quality of life and functionality for years after the injury. In fact, half of the hospitalized TBI patients develop TBI-related long-term or permanent disability [18], and over 70% of people diagnosed with severe TBI require long-lasting care and support [19]. In addition, TBI is strongly associated with subsequent disabling neurological disorders including Alzheimer's and Parkinson's diseases [20].

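### The only named between-group test is a three-group MANOVA of EVestG biofeatures, whose overall results do not identify an rTMS effect; Treatment v Sham is stated but not specified, and the clinical outcomes have no between-group test, primary outcome or efficacy visit

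*Combined protocol and SAP*

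**What the plan says.** - **Named test.** Data analysis (Statistical Analysis, Clustering, Decision Making and Validation) states that "the multivariate Analysis of Variance (MANOVA) statistical test will be run to determine the significant differences of any of the extracted biofeature measures". The comparisons that this test is to cover are described only as "between the sessions and the Control Group and the Treatment and Sham Groups". It names no contrast, no interaction and no handling of baseline.
- **Two-arm comparison.** The EVestG Biofeature Extraction paragraph says that biofeatures "from the recorded signal will be compared between Sham and Treatment Groups". No test, visit or baseline handling is given.
- **Significance rule.** "In all instances, a p-value less than 0.05 is considered significant".
- **Clinical efficacy.** Objective 3 (Theme 1) is to "examine the efficacy of rTMS treatment on the post-TBI symptoms by standard clinical and neuropsychological assessments by statistical analysis". The same objective includes "Record spatio-temporal assessments before and after treatment sessions". Data analysis uses the neuropsychological scores only for correlation with biofeatures and as a check on the diagnostic and monitoring algorithms.
- **Outcomes and visits.** For RPQ, MoCA, MADRS and Stroop, "Patients with TBI will go through all above mentioned assessments four times, similar to EVestG assessments". Table 1 lists these and the spatio-temporal assessment at baseline and weeks 4, 8 and 12. None is called primary, and no visit is designated for efficacy.
- **Decision that depends on it.** Research Plan and Methods, and the closing paragraph of Exclusion Criteria for all Participants, make the offer of active treatment to the Sham Group depend on a benefit over sham.

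**The concern.** Randomisation is between Treatment and Sham. The 20 healthy controls are not randomised and receive no stimulation. An overall test across all three groups therefore mixes the randomised comparison with the difference between TBI and healthy people. An overall test across sessions mixes it with change that both arms share. The Rationale allows for such change: after TBI, "the fastest improvement occurs in the first six months after injury and the patient may continue to get better" for up to two years.

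An interaction across all three groups does not cure this. Recovering patients set against stable controls produce a group-by-session effect even when the two patient arms change identically.

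At stake is the statement that rTMS is effective, and with it the Sham Group offer. For symptoms, no specified analysis answers that question. The blanket p<0.05 rule leaves room to choose afterwards among several scales and visits.

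**Working it through.** The plan gives no effect size, SD, correlation or power, so there is no stated figure to reproduce. All effect sizes and correlations below are reviewer assumptions.

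**Inputs from the documents.** 10 Treatment, 10 Sham and 20 controls (Study Population/Participants); one baseline and three later assessments (EVestG Measurement; Table 1); p<0.05 (Data analysis). Tests are taken as two-sided, which the plan does not state.

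**1. Overall group test at one session, Treatment equal to Sham.** Take one feature with group means (d, d, 0) in SD units. The grand mean is d/2, so the noncentrality is 20(d/2)² + 20(d/2)² = 10d², with 2 and 37 df.

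| TBI-control gap d | 10d² | Rejects, one feature | Rejects, three uncorrelated features, gap on one |
|---|---|---|---|
| 0.5 | 2.5 | 0.255 | 0.158 |
| 0.8 | 6.4 | 0.576 | 0.371 |
| 1.0 | 10 | 0.781 | 0.567 |

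The last column uses Wilks' lambda (40,000 simulations).

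**2. Session tests, both arms improving equally.** Patients in both arms change by 0.5 SD at all three later sessions; controls do not change. Simulated rejection rates at within-person correlation 0.5 / 0.7:

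| Test | One feature | Three uncorrelated features, one changing |
|---|---|---|
| Session, groups weighted equally | 0.475 / 0.707 | 0.259 / 0.434 |
| Session, participants weighted equally | 0.310 / 0.487 | 0.165 / 0.270 |
| Three-group-by-session | 0.222 / 0.358 | 0.127 / 0.190 |
| Treatment v Sham by session | 0.050 / 0.050 | 0.052 / 0.050 |

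A second set-up used three features correlated at 0.5, all of them shifted. It agreed: two-arm contrasts with no rTMS effect rejected in 0.044 to 0.057 of trials in every scenario, while with shared recovery of 0.5 or 1.0 SD the three-group test of change rejected in about 0.21 to 0.77.

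**3. Clinical outcomes tested at each visit at unadjusted p<0.05.** Four instruments × 3 visits = 12 tests, with one score each. If independent, the chance of at least one false positive is 1 − 0.95¹² = 0.460. Adding one spatio-temporal score gives 15 tests and 1 − 0.95¹⁵ = 0.537. Simulated t-tests with 10 per arm:

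| Common correlation | 0.3 | 0.5 | 0.7 | 0.9 |
|---|---|---|---|---|
| 12 tests | 0.402 | 0.330 | 0.243 | 0.142 |
| 15 tests | 0.466 | 0.373 | 0.270 | 0.149 |

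**4. What 10 per arm can show at one visit.** For a true effect of 0.8 SD without baseline adjustment, the noncentrality is 0.8 × √(10/2) = 1.79 with 18 df. Power is 0.395, so the effect is missed 0.605 of the time. The 95% CI half-width is 2.101 × √0.2 = 0.94 SD. With ANCOVA, the half-width is 2.110 × √(0.2 × (1 − r²) × (1 + 1/16)), where r is the correlation with baseline:

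| r | Simulated power | Missed | Half-width (SD) |
|---|---|---|---|
| 0.3 | 0.408 | 0.592 | 0.93 |
| 0.5 | 0.475 | 0.525 | 0.84 |
| 0.7 | 0.628 | 0.372 | 0.69 |

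**The case against.** Several points on the other side stand.

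- **The MANOVA model can hold the right contrast.** It includes sessions and keeps Treatment and Sham as separate groups. A reader might infer that it is incapable of isolating rTMS. The text does not support that: a Treatment-v-Sham contrast of change within the model would do it, and a Sham-Treatment comparison of biofeatures is stated. The plan also never says that an overall result will be read as efficacy. The rates in steps 1 and 2 apply only if it is.
- **Shared recovery is possible, not established.** The Rationale also says that many survivors have persisting symptoms, and those are the patients enrolled. The 0.5 SD is an assumption. A lower limit of two months since injury appears only in Objective 1; Study Population/Participants and Inclusion Criteria for Patients give the last 12 months with no lower limit.
- **The 12 or 15 clinical tests are not a stated plan.** The counts assume one score per instrument, and the plan defines none for Stroop or the spatio-temporal assessment. A reader might take 46% as the plan's error rate; it is what would follow if the blanket rule were applied to each scale at each visit.
- **The schedule discrepancies do not block naming a visit.** A reader might infer that they do. EVestG Measurement numbers the four assessments, so one can be named by number now.
- **This is a pilot.** That excuses low power. It does not excuse leaving the efficacy comparison undefined when a decision for Sham participants depends on it.

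None of these points supplies a between-group analysis for the clinical outcomes.

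**Conclusion.** The point holds as one of specification. The overall group, session and three-group-by-session results of the named MANOVA do not identify an rTMS effect. The Treatment-v-Sham comparison that would identify it lacks a test, baseline handling and a visit. RPQ, MoCA, MADRS, Stroop and the spatio-temporal assessment have no named between-group test, primary outcome or efficacy visit.

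For size, with no rTMS effect and the one-feature assumptions in the working, the overall tests reject in 22% to 78% of trials and a two-arm test in 5%. The exact rates depend on assumed gaps, recovery and correlations. The direction does not, provided that TBI patients differ from controls or recover in parallel. The gaps in the clinical analysis rest on the text alone.

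**What to change.** In Data analysis:

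1. **Treatment comparison.** Estimate the rTMS effect in the two randomised arms only, as the Treatment-minus-Sham difference with 95% CI at each post-baseline assessment, by ANCOVA with arm and the outcome's own baseline value. A mixed model is acceptable. Apply it to the clinical scales, the spatio-temporal assessment and a short list of biofeatures. Fix that list, and the Stroop and spatio-temporal scores, before unblinding.
2. **Main outcome and visit.** Before unblinding, name one clinical outcome and one numbered assessment (2, 3 or 4 in EVestG Measurement) for the main treatment comparison. The choice is the sponsor's.
3. **Significance rule.** For Treatment v Sham, limit p<0.05 to that outcome and assessment, and report all other comparisons as estimates with 95% CIs. Because this is a pilot, present the estimate and CI as the main result.
4. **Three-group work.** Keep the MANOVA and discriminant analysis for the EVestG diagnostic and monitoring aims, and state that they are not evidence of efficacy.

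**Cost.** No new data are needed, but the scores and the biofeature list must be defined. The covariate uses one degree of freedom and gains little if the baseline correlation is near 0.3 (power 41% against 40%). Secondary outcomes cannot be declared significant on their own. With 10 per arm, a true 0.8 SD effect would be missed about 60% of the time unadjusted, or about 37% to 59% with ANCOVA, so the plan should say that a non-significant result is not evidence of no effect.

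**Separately, and not as a precondition.** rTMS Treatment Procedure gives 13 treatments, while Table 1 gives 5 + 5 + 2 = 12. Time since injury is two to 12 months in Objective 1, but the last 12 months in Study Population/Participants and Inclusion Criteria for Patients. These passages must be reconciled.

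### The EVestG MANOVA has no defined outcome vector: the features described far outnumber the error degrees of freedom, and the workable alternatives are unadjusted or select on the effect being tested

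*Combined protocol and SAP*

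**What the plan says.** Under Data analysis, the paragraph on statistical analysis and validation states that "the multivariate Analysis of Variance (MANOVA) statistical test will be run to determine the significant differences of any of the extracted biofeature measures" between sessions and among the Control, Treatment and Sham Groups, with 0.05 as the threshold throughout. Features found significant then go into a discriminant analysis with leave-one-out. The biofeature paragraph above it adds: "The features extracted from all tilts will be investigated to determine biofeatures specific to a concussion". It names the mean, variance, fractal dimension, kurtosis and skewness as examples, together with the probability density function, and leaves the list open.

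The recording design is spread over two sections. Objective 4 reads "Record EVestG data with all its seven current stimuli at baseline". EVestG Measurement describes the movements as "up/down translation and a horizontal rotation to the right and return to center (RTC) in both sitting upright and supine positions, and side tilts" to each side. It records from both ears and names six segments of interest per recording: BGi, onAA, onBB and the three return-to-center equivalents. There are four sessions.

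For group sizes, Study Population/Participants gives "A total of 20 individuals with a clear diagnosis of TBI within the last 12 months", split 10 and 10 between Treatment and Sham, and "20 age-and-gender-matched cognitively healthy volunteers will be recruited as controls for the EVestG assessment".

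Objective 5 aims to find the EVestG measures that best show change due to rTMS. It gives no selection rule and no limit on their number. No multiplicity adjustment appears anywhere.

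**The concern.** MANOVA inverts the within-group covariance matrix of the outcomes, so the number of outcomes may not exceed the error degrees of freedom. The plan describes hundreds of candidate outcomes for 40 people and does not say which of them enter the test. The analyst will have to choose when the data are in hand, and the plan does not stop that choice from being made after the groups are known.

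There is also a mismatch of purpose. An omnibus MANOVA p-value says that the groups differ on some combination of outcomes. It does not say which features differ, yet the next step needs a list of significant features for the discriminant analysis.

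At stake is whether a p-value below 0.05 for EVestG between Treatment and Sham could be interpreted at all, and whether the features passed on to classification are more than chance findings.

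**Working it through.** The documents give no feature count, degrees of freedom or power, so there is no stated figure to reproduce.

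**Feature count per session** = stimuli × ears × segments × scalar statistics.
- Seven stimuli (Objective 4): 7 × 2 × 6 × 5 = 420.
- Six stimuli (a plain count of EVestG Measurement: two movements in two positions, plus two side tilts): 6 × 2 × 6 × 5 = 360.
- Smallest reading tried (six stimuli, ears averaged, three segments, three statistics): 6 × 1 × 3 × 3 = 54.
- Largest (seven stimuli, two ears, six segments, six statistics): 7 × 2 × 6 × 6 = 504.

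**Error degrees of freedom** = people − groups, with full enrolment and no dropout.
- Three groups: 40 − 3 = 37.
- Treatment versus Sham alone: 20 − 2 = 18.

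Every count from 54 to 504 exceeds both limits. Simulation confirmed the rank of the within-group matrix as 37 and 18 at 360 and 420 features. Treating the four sessions as independent rows, which repeated measures are not, gives 160 − 12 = 148 for three groups and 80 − 8 = 72 for two. Both are still below 360.

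**Which subsets run**

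| Outcome set | Features | Three groups (37 df) | Treatment v Sham alone (18 df) |
|---|---|---|---|
| One stimulus, segment and ear | 5 | runs | runs |
| One stimulus and ear | 6 × 5 = 30 | runs | singular |
| One stimulus, both ears | 2 × 30 = 60 | singular | singular |

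**Cost of splitting into five-feature tests.** Tests per session: 7 × 2 × 6 = 84, or 6 × 2 × 6 = 72. False positives expected under the null at 0.05: 84 × 0.05 = 4.2, or 72 × 0.05 = 3.6. If the tests were independent, the chance of at least one is 1 − 0.95^84 = 98.7%, or 1 − 0.95^72 = 97.5%. Features from one recording are probably correlated, which lowers that chance but leaves the expected number unchanged.

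**Power where the test does run.** Assume 10 versus 10, one feature differing by 1.2 SD, and the other features independent with no effect. The noncentrality is (10 × 10/20) × 1.2² = 7.2. With error df ν and p features, the F test has p and ν − p + 1 degrees of freedom.

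| Features p | Contrast in three-group model (ν = 37) | Two arms alone (ν = 18) |
|---|---|---|
| 3 | 55% | 49% |
| 5 | 44% | 36% |
| 10 | 29% | 19% |
| 15 | 21% | 10% |

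A single feature tested in the two arms alone has 72% power at 0.05, and 53% at 0.05/3. The 1.2 SD is an assumption. At 1.0 SD, the two-arm figures for 1, 3, 5, 10 and 15 features are 56%, 35%, 26%, 14% and 8%.

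**The case against.** The strongest reply is that the plan never says all features enter one model. It looks for differences in any of the measures, refers afterwards to significant features, intends in Objective 5 to extract the best measures and in Objective 6 to reduce the stimuli, and captions a pilot figure that separates groups on two features. A reader might infer that the planned MANOVA cannot be run at all. The documents do not support that, because small outcome sets are computable. This part of the objection stands. Nor is 420 the plan's own number: it is a product of counts from different sections, with an open feature list and an unsettled number of stimuli.

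Three further limits also stand:
- The discriminant analysis takes only features already found significant, so it cannot be said to face hundreds of inputs.
- MANOVA is not the only analysis named. The correlation and clustering analyses do not depend on it, and clinical efficacy is assessed under Objective 3 with other instruments.
- A Treatment versus Sham contrast inside the three-group model uses 37 degrees of freedom, so power falls less steeply than the two-arm figures suggest. Correlated features could raise it. With correlation 0.5, power for three features is 68% even on 18 degrees of freedom.

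The power argument alone does not favour the remedy much: 53% at the strictest Holm step against 49% for a three-feature MANOVA.

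The reply does not supply a valid route through the section as written. Splitting has no error control. Selecting by Objective 5 uses the treatment change to pick the features in which that change is then tested. Pilot status does not remove the problem while 0.05 remains the decision rule.

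**Conclusion.** The concern holds in a conditional form. The EVestG outcome vector is undefined. A joint per-session test of all described features is singular on every reading examined. A split into five-feature tests yields about 4 expected false positives per session, and selection on the rTMS change biases the test that follows. In no case does the omnibus p-value name the features that the next step needs. This is more than missing detail, because each way of following the section fails for a different reason.

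The figures of 37 and 18 assume 40 people with complete data, and dropout lowers them. The counts of 360 and 420 assume two ears, six segments and five statistics. The near-certainty of a false positive assumes independent tests. The conclusion reaches the EVestG group comparison and the features it hands to the discriminant analysis. It does not reach the clinical and neuropsychological outcomes, the correlation analysis or the clustering.

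**What to change.** Before assignments are revealed, the sponsor should amend the analysis text as follows:

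1. Fix at most three EVestG summary features by a written rule that does not use Treatment or Sham labels. Suitable bases are blinded pooled patient data, or reliability across the four sessions that Objective 8 already schedules for controls.
2. Replace the MANOVA, for the comparison that carries a significance claim, with one Treatment versus Sham test per listed feature, Holm-adjusted. State the session at which the test is made and how the other sessions enter, since testing every session would enlarge the family.
3. Keep all other features, including the stimulus-level results that Objective 6 needs, and label them exploratory. Averaging over all stimuli should not be the only summary kept, because it would remove what Objective 6 examines.
4. State the number of stimuli consistently between Objective 4 and EVestG Measurement.

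No visit, recording or participant is added. The price is that features off the list support only exploratory statements, and a reliability rule favours stable features, which may not be the most responsive to treatment.
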